8.5 Follow-up of Adverse Events

All adverse events will be followed with appropriate medical management until resolved. Patients removed from study for unacceptable adverse events will be followed until resolution or stabilization of the adverse event. For selected adverse events for which administration of the investigational drug was stopped, a re-challenge of the subject with the investigational drug may be conducted if considered both safe and ethical by the Investigator.

8.6 Adverse Events Monitoring

All adverse events, whether or not unexpected, and whether or not considered to be associated with the use of the study drug, will be entered into OnCore®, as noted above.

The Investigator will assess all adverse events beginning at the time of informed consent and determine reportability requirements to the UCSF Data and Safety Monitoring Committee (DSMC) and UCSF's Institutional Review Board, the Institutional Review Board (IRB); and, when the study is conducted under an Investigational New Drug Application (IND), to the Food and Drug Administration (FDA) if it meets the FDA reporting criteria.

All adverse events entered into OnCore® will be reviewed by the Helen Diller Family Comprehensive Cancer Center Site Committee on a weekly basis. The Site Committee will review and discuss at each weekly meeting the selected toxicity, the toxicity grade, and the attribution of relationship of the adverse event to the administration of the study drug(s).

All grade(s) 3-5 adverse events entered into OnCore® will be reviewed on a monthly basis at the Site Committee meetings. The Site Committee will review and discuss the selected toxicity, the toxicity grade, and the attribution of relationship of the adverse event to the administration of the study drug(s).

In addition, all suspected adverse reactions considered "serious" entered into OnCore®, will be reviewed and monitored by the Data and Safety Monitoring Committee on an ongoing basis and discussed at DSMC meetings, which take place every six weeks.

For a detailed description of the Data and Safety Monitoring Plan for a Multicenter Phase 2 or 3 Institutional Study at the Helen Diller Comprehensive Cancer Center please refer Appendix 4 Multicenter Institutional Studies.

8.7 Expedited Reporting

Reporting to the Data and Safety Monitoring Committee

If a death occurs during the treatment phase of the study or within 30 days after the last administration of the study drug(s) and it is determined to be related either to the study drug(s) or to a study procedure, the Investigator or his/her designee must notify the DSMC Chair (or qualified alternate) within 1 business day of knowledge of the event. The contact may be by phone or e-mail.

Reporting to UCSF Institutional Review Board (IRB)

The Principal Investigator must report events meeting the UCSF IRB definition of “Unanticipated Problem” (UP) within 10 business days of his/her awareness of the event.

Expedited Reporting to the Food and Drug Administration

If the study is being conducted under an IND, the Investigator is responsible for determining whether or not the suspected adverse reaction meets the criteria for expedited reporting in accordance with Federal Regulations (21 CFR §312.32).

The Investigator must report in an IND safety report any suspected adverse reaction that is both serious and unexpected. The Investigator needs to ensure that the event meets all three definitions:

- Suspected adverse reaction
- Unexpected
- Serious

If the adverse event does not meet all three of the definitions, it should not be submitted as an expedited IND safety report.

The timeline for submitting an IND safety report to FDA is no later than **15 calendar days** after the Investigator determines that the suspected adverse reaction qualifies for reporting (21 CFR 312.32(c)(1)).

Any unexpected fatal or life-threatening suspected adverse reaction will be reported to FDA no later than **7 calendar days** after the Investigator’s initial receipt of the information (21 CFR 312.32(c)(2)).

Any relevant additional information that pertains to a previously submitted IND safety report will be submitted to FDA as a Follow-up IND Safety Report without delay, as soon as the information is available (21 CFR 312.32(d)(2)).

Reporting to Pharmaceutical Companies providing Study Drug

Any serious adverse event occurring after the patient has provided informed consent and until 4 weeks after the patient has stopped study participation must be reported. This includes the period in which the study protocol interferes with the standard medical treatment given to a patient (e.g. treatment withdrawal during washout period, change in treatment to a fixed dose of concomitant medication). As soon as an Investigator becomes aware of an AE that meets the definition of “serious”, this should be documented to the extent that information is available. This includes serious, related, labeled (expected) and serious, related, unlabeled (unexpected) adverse experiences. All deaths during treatment or within 30 days following completion of active protocol therapy must be reported within 24 hours. Serious adverse events occurring more than 4 weeks after study discontinuation need only be reported if a relationship to the study drug (or therapy) is suspected.

Investigator shall notify the appropriate pharmaceutical company **within twenty-four (24) hours** of making such discovery by submitting the completed SAE report form and any other pertinent SAE information as indicated on the SAE reporting form. Applicable events will be reported to the IRB and FDA as per current policies.

This report must be submitted by Institution to the appropriate pharmaceutical company even if it is not felt to be drug related:

- [REDACTED]
 - [REDACTED]
 - [REDACTED]
- [REDACTED]
 - [REDACTED]
 - [REDACTED]
- [REDACTED]
 - [REDACTED]
 - [REDACTED]
 - [REDACTED]
 - [REDACTED]
- [REDACTED]
 - [REDACTED]
 - [REDACTED]
 - [REDACTED]
- For Comparator Drugs/Secondary Suspects (Concomitant Medications), all serious adverse experiences will be forwarded to the product manufacturer by the investigator.
- Pregnancy (for a subject or for the partner of a subject) that occurs during study participation, although not itself an SAE, should be reported. To ensure patient safety each pregnancy must also be reported to the appropriate pharmaceutical company within 24 hours of learning of its occurrence. The pregnancy should be followed up to determine outcome, including spontaneous or voluntary termination, details of birth, and the presence or absence of any birth defects, congenital abnormalities or maternal and newborn complications.

SAEs that must be recorded on an SAE Reporting form include the following:

- all SAEs that occur after informed consent and through 30 days after the decision to discontinue study treatment (or the date the subject is deemed to be a screen failure);
- any SAEs assessed as related to study treatment or study procedures, even if the SAE occurs more than 30 days after the decision to discontinue study treatment;
- although most hospitalizations necessitate reporting of an SAE, some hospitalizations do not require SAE reporting, as follows:
 - elective or previously scheduled surgeries or procedures for pre-existing conditions that have not worsened after initiation of treatment (e.g., a previously scheduled ventral hernia repair);
 - pre-specified study hospitalizations for observation; or
 - events that result in hospital stays of fewer than 24 hours and that do not require admission (e.g., an emergency room visit for hematuria that results in a diagnosis of cystitis and discharge to home on oral antibiotics). SAEs must, however, be reported for any surgical or procedural complication resulting in prolongation of the hospitalization.

9 Statistical Considerations and Evaluation of Results

This is a phase II, prospective, multicenter, single arm trial to test the hypothesis that targeting specific kinase fusions in melanoma with pre-specified kinase inhibitors will result in objective tumor response. Patients will be screened for one of the eligible fusion proteins under a separate protocol, and if identified will be treated in this study in one of six baskets (ALK, NTRK, ROS1, RET, MET, or BRAF kinase fusions). The primary endpoint is composite (all fusion types analyzed together) confirmed objective response as defined as a complete or partial response as per RECIST v1.1 criteria. Standard therapies such as IL-2 and ipilimumab have shown response rates of approximately 10%. The newly approved immunotherapy pembrolizumab has a response rate of approximately 30%.

A 2-stage optimal design will be employed in which a 10% response rate is considered not promising, a 30% response rate is considered promising, and the probabilities of a type I error (falsely accepting a non-promising therapy) and type II error (falsely rejecting a promising therapy) are set at 0.05 and 0.1, respectively. In this scenario, the maximum trial size would be 35 evaluable patients. Evaluable patients would be those with baseline staging, treatment for at least one cycle (with at least 90% of intended doses administered during cycle 1), and at least one post-baseline staging scan while on treatment. We estimate a drop-out rate of 20%, and therefore 44 patients will be enrolled and started on treatment. In the first stage of this design, 11 patients will be accrued. If 1 or fewer patients achieve a response among the initial 11 patients, the trial will be terminated. If at least 2 patients achieve a response among these 11 patients, then an additional 24 patients will be accrued to the second stage. If 6 or fewer patients achieve a response in the second stage, the trial will be terminated. Under these conditions, if the response rate is 0.1, the probability of ending the trial during stage 1 is 0.70. If the true response rate is 0.3, the probability that the trial will be stopped in stage I is 0.11.

Analysis of study results will be carried out by the study statistician and will include overall response rate (ORR) estimations of ALK, NTRK, ROS1, RET, MET, and BRAF rearrangement-positive patients.

Clinical benefit rate (CBR) defined as the proportion of patients achieving a complete response (CR) or partial response (PR) or stable disease (SD) for > 24 weeks will be estimated for each arm along with a 95% confidence interval.

Progression free survival (PFS) defined as the time from treatment start to the progression or death and overall survival defined as the time from treatment start to death will be estimated using Kaplan-Meier methodology.

Frequencies of toxicities will be tabulated according to CTCAE v4.03 to assess drug safety and tolerability.

Exploratory endpoints will include expression levels (reported as percentage by IHC) of the fusion kinase protein. Measures taken at baseline as well as after four weeks of therapy will be summarized. Changes in expression level will be assessed between baskets using a paired t-test if data permit. For patients who progress on therapy, an additional biopsy may be obtained and will be compared with baseline expression levels if data permit. This will inform on molecular mechanisms of resistance for patients who progress while on therapy.

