Secondary Objectives	
 To estimate tumor stability in kinase fusion melanoma patients treated with kinase inhibitors matched to the activated fusion partner. To estimate survival in kinase fusion melanoma patients treated with kinase inhibitors matched to the activated fusion partner. To examine the safety and tolerability of kinase inhibitors in patients with the kinase fusion targets.
Exploratory Objectives	
 To explore molecular mechanisms of resistance for patients who progress on therapy.
Primary Endpoint	
 Confirmed ORR by RECIST v1.1 at 24 weeks.
Secondary Endpoints	
 Confirmed CBR (defined as CR or PR or SD for >24 weeks). Determination of PFS and OS. Evaluation of the adverse effect profile, using CTCAE v4.03, of each kinase inhibitor.
Exploratory Endpoints	
 Exploratory endpoints to include assessment of expression levels of the fusion kinase protein, reported as percentage by IHC staining. Measures taken at baseline and after 4 weeks of therapy will be summarized. Changes in expression level will be assessed between baskets using a paired t-test if data permit. For patients who progress on therapy, an additional biopsy may be obtained and will be compared with baseline expression levels if data permit.
Study Design	This is a phase II multi-center prospective basket trial designed to test the hypothesis that targeting specific kinase fusions in metastatic melanoma with pre-specified kinase inhibitors will result in objective tumor shrinkage and durable response. The study design is a 2 stage optimal design with a sample size of N=35, with n1=11 during stage I and n2=24 during stage II. If 1 or fewer responses are observed during stage I, the trial will be stopped. If 6 or fewer responses are observed by the end of stage II, the trial will be stopped.

Number of patients	Estimating a drop-out rate of 20%, we anticipate enrolling 44 patients to accrue 35 evaluable patients.
Study Drugs	Capmatinib, Entrectinib, Ceritinib, Regorafenib
Safety Assessments	Physical exam with evaluation of vital signs, performance status, and toxicity grading as per CTCAE v4.03. Clinical laboratory evaluations including CBC, CMP.
Efficacy Assessments	ORR and CBR to be assessed as per RECIST v1.1 criteria.

List of Abbreviations

AE	adverse event
ALT	alanine aminotransferase
AST	aspartate aminotransferase

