4.2 Number of Subjects

We anticipate enrollment of 35 evaluable patients to this study. Identification of a fusion kinase is required for eligibility and testing for fusion kinases is not standard of care. A separate UCSF research protocol will screen melanoma patients in need of treatment who are wild-type for BRAF mutation for fusion kinases (PI: [name]).

The sample size is based on a 2-stage Simon's optimal design using ORR at 24 weeks as primary efficacy endpoint. We assume that a response rate of 10% would be unacceptable and a response rate of 30% would be considered clinically meaningful. Under type I error of 0.05 and type II error of 0.15, in the first stage of this design, 11 patients will be accrued. If 1 or fewer patients achieve a response among the initial 11 patients, the trial will be terminated. If at least 2 patients achieve a response among these 11 patients, then an additional 24 patients will be accrued to the second stage. If 6 or fewer patients achieve a response, then the trial will be terminated. Under these conditions, if the response rate is 0.1, the probability of ending the trial during stage 1 is 0.70. If the true response rate is 0.3, the probability that the trial will be stopped in stage I is 0.11.

If 35 evaluable patients with follow-up of at least 12 months are enrolled, but fewer than 5 patients are assigned to a given drug, the study will continue to enroll patients until we have enrolled at least 5 patients for each of the 4 study drugs with a max of 50 patients enrolled.

We anticipate enrollment of 35 evaluable patients to this study. Evaluable patients would be those with baseline staging, treatment for at least 8 weeks, and at least one post-baseline staging scan while on treatment. We estimate a drop-out rate of 20%, and therefore 44 patients will be enrolled and started on treatment. Kinase fusion melanoma prevalence is currently estimated at 10% of BRAF/NRAS WT melanomas, thus we anticipate screening 440 patients to enroll 44 patients.

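### Section 9 states a type II error of 0.10 for a design whose type II error is 0.149, and its final cut-off, read literally, counts only stage 2 responses

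*Combined protocol and SAP*

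**What the plan says.** The design appears in three places: the Abstract, Section 4.2 and Section 9. All three give 11 patients in stage 1, 24 in stage 2, a stop at 1 or fewer responses in stage 1, and a final cut-off of 6. Sections 4.2 and 9 use the same null and target response rates. In Section 9's words, "a 10% response rate is considered not promising, a 30% response rate is considered promising". Both also give the same stage 1 stopping probabilities, 0.70 at a 10% response rate and 0.11 at 30%.

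They differ on two points.

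- **Type II error.** Section 9: "type II error (falsely rejecting a promising therapy) are set at 0.05 and 0.1, respectively". Section 4.2: "Under type I error of 0.05 and type II error of 0.15".
- **What the final cut-off counts.** Section 9: "If 6 or fewer patients achieve a response in the second stage, the trial will be terminated". Abstract: "If 6 or fewer responses are observed by the end of stage II, the trial will be stopped". Section 4.2 gives the cut-off of 6 without a denominator, directly after mentioning the 24 further patients.

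**The concern.** One set of stage sizes and cut-offs has one type II error at a given target rate, so 0.10 and 0.15 cannot both describe this design. If 0.15 is right, anyone relying on Section 9 believes the trial has 90% power when it has 85%.

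The second difference can change the trial's conclusion. The sentence before Section 9's final rule assigns 24 patients to the second stage, so the plain reading is 6 or fewer of those 24, with stage 1 responders left out. A result of 3/11 followed by 6/24 (9/35, 26%) would pass under the Abstract and fail under Section 9. This is the primary go/no-go rule of a single-arm trial. Choosing between the two readings after seeing the data would undo its pre-specification.

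**Working it through.** **Inputs.** p0 = 0.10, p1 = 0.30, n1 = 11, n2 = 24, stage 1 stop at ≤ 1, final cut-off 6, type I error 0.05 (Sections 4.2 and 9). The type I error is taken as one-sided, as is usual for this design; the documents do not say. X1 and X2 are the independent binomial response counts in stages 1 and 2.

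**Step 1: reproduce the stated stage 1 figures.** P(X1 ≤ 1) = (1−p)^11 + 11·p·(1−p)^10.

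- p = 0.1: 0.3138 + 0.3835 = 0.697 (stated 0.70).
- p = 0.3: 0.0198 + 0.0932 = 0.113 (stated 0.11).

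Both agree, so the 11-patient first stage is the one that the plan's figures describe.

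**Step 2: a bound from Section 9's own figures.** Stopping in stage 1 when p = 0.3 is a false rejection. Type II error is therefore at least 0.113 before stage 2 begins, and no stage 2 rule can bring it down to 0.10.

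**Step 3: the cumulative rule.** P(pass) = Σ over x = 2,…,11 of P(X1 = x)·P(X2 ≥ 7 − x).

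- p = 0.1: 0.0422 (type I error).
- p = 0.3: 0.8510, so type II error is 1 − 0.8510 = 0.149. Of this, 0.113 arises in stage 1 and 0.149 − 0.113 = 0.036 at the final analysis.

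This matches Section 4.2's 0.15 and not Section 9's 0.10.

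**Step 4: which optimal design is this?** A full search of Simon designs up to N = 45 with type I error ≤ 0.05 gives:

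| Type II limit | Optimal design | Type I error | Type II error | Expected N at p = 0.1 |
|---|---|---|---|---|
| 0.15 | 1/11, then 6/35 | 0.042 | 0.149 | 11 + 24 × (1 − 0.697) = 18.3 |
| 0.10 | 2/18, then 6/35 | 0.047 | 0.098 | 18 + 17 × (1 − 0.734) = 22.5 |

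The two designs share the maximum of 35 and the final cut-off of 6, so a check on the maximum sample size alone would not show the mismatch. Dropping the interim look does not rescue 0.10 either: a single-stage test needing 7 of 35 has power 0.935, but its type I error is 0.055.

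**Step 5: Section 9's final rule taken literally.** P(pass) = P(X1 ≥ 2)·P(X2 ≥ 7 of 24).

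- p = 0.1: 0.3026 × 0.00746 = 0.0023.
- p = 0.3: 0.8870 × 0.6114 = 0.542.

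Any trial that passes the literal rule has at least 2 + 7 = 9 responders and so also passes the cumulative rule. At a true 30% rate, the two readings therefore disagree with probability 0.851 − 0.542 = 0.309.

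**The case against.** The strongest objection is that the 54% rests on an unlikely reading. Section 9 sets type I error at 0.05 and calls the plan a two-stage optimal design, but the literal rule has type I error 0.0023. The Abstract counts cumulatively, and Section 4.2 does not restrict the count to the second stage. The phrase may be loose wording for the second-stage analysis. This is persuasive as to intent: the numerical design is sound, and 54% is what follows only if Section 9 is applied as written. It does not remove the conflict, because an analyst would follow the statistical section and nothing says that the Abstract overrides it.

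A second objection is that the 0.10 is a reporting slip. Stage sizes, cut-offs, the enrolment target of 44 and the stage 1 probabilities are the same in Sections 4.2 and 9, and Section 4.2 already has the right value. That is true: no stopping decision depends on the stated type II error, and the overstatement of power is 0.90 − 0.851 = 4.9 percentage points. On its own this half would be a consistency correction. The wording of the cut-off carries the greater weight.

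**Conclusion.** The concern holds. Section 9's type II error of 0.10 is wrong for the design it describes; the exact value is 0.149, as Section 4.2 has it to rounding. The final cut-off is stated inconsistently. Under the cumulative count the design has type I error 0.042 and power 85%; under Section 9's literal wording these are 0.0023 and 54%.

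These figures assume independent responses with a common response rate across the pooled baskets, and a decision based on exactly 35 evaluable patients. Section 4.2 allows enrolment to continue to a maximum of 50 so that each drug has at least 5 patients. The figures do not cover a decision that includes those later patients. How 0.10 came to stand beside the 11-patient first stage cannot be told from the documents.

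**What to change.** 1. In Section 9, change the type II error to 0.15 (power 85%), in line with Section 4.2.
2. In Section 9, apply the final cut-off to both stages together: the therapy is not considered promising if 6 or fewer of the 35 evaluable patients from stages 1 and 2 combined respond. Put the same denominator in Section 4.2.
3. State whether patients enrolled beyond 35 to fill a drug group enter this decision.

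Items 1 and 2 are wording corrections. They need no extra patients, and the only cost is that Section 9 states 85% power instead of 90%.

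If 90% power is really wanted, the 2/18, 6/35 design gives 0.902 at the same maximum of 35. That is a redesign: the futility look comes 7 patients later (18 instead of 11), and the expected sample size at a 10% response rate rises from 18.3 to 22.5. It would have to be adopted before stage 1 is analysed. The stated stage 1 probabilities of 0.70 and 0.11 suggest that the 11-patient first stage was intended, so the wording correction is the natural choice.

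### Section 9 applies the final boundary of 6 responses to the second stage alone; taken literally, power at a 30% response rate is 0.54, not 0.85

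*Combined protocol and SAP*

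**What the plan says.** The final boundary appears in three places, worded differently each time.

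- **Section 9 (Statistical Considerations):** "If 6 or fewer patients achieve a response in the second stage, the trial will be terminated". The sentence before it says that 24 further patients enter the second stage.
- **Abstract, Study Design:** "If 6 or fewer responses are observed by the end of stage II, the trial will be stopped".
- **Section 4.2 (Number of Subjects):** "If 6 or fewer patients achieve a response, then the trial will be terminated", with no stage named.

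The type II error also differs. Section 9 has "type II error (falsely rejecting a promising therapy) are set at 0.05 and 0.1, respectively"; Section 4.2 has "Under type I error of 0.05 and type II error of 0.15".

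The rest agrees. Sections 4.2 and 9 both describe a two-stage optimal design (Section 4.2 names Simon's), with 11 then 24 patients, a stop at 1 or fewer responses in the first 11, response rates of 10% and 30%, and stage I stopping probabilities of 0.70 and 0.11. Nothing in the documents says which wording of the final boundary prevails.

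**The concern.** In Simon's design the final boundary is a total over both stages. Section 9 as written restricts it to the 24 second-stage patients and so discards every stage I response. That is a different and much stricter rule.

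The sentence decides whether the primary endpoint is met, and the same data can pass under one section and fail under another. With 2/11 and 5/24 the total is 7/35: a pass under the Abstract, a failure under Section 9. With 5/11 and 6/24 the total is 11/35 (31%, above the 30% target), and Section 9 still calls the trial negative. If the reading were chosen after the data were known, the choice would itself determine the primary conclusion.

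Section 9's own type II error does not help a reader recover the intended rule, because 0.1 fits neither reading.

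**Working it through.** **Inputs.** Unacceptable rate 0.10, target rate 0.30, type I error 0.05 (Sections 4.2 and 9). Type II error 0.15 (Section 4.2) or 0.1 (Section 9). Stage sizes 11 and 24, boundaries 1 and 6 (Abstract, Sections 4.2 and 9). X1 is the number of responses among the first 11 patients and X2 the number among the next 24; both are binomial with true rate p. All probabilities are exact.

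**1. Reproduce the plan's own figures.** P(X1 ≤ 1) is 0.697 at p = 0.1 and 0.113 at p = 0.3, matching the stated 0.70 and 0.11. These depend on stage I only. They confirm the 11 and the 1, but say nothing about how the 6 is counted.

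**2. Cumulative rule: at least 2/11, then at least 7/35 in total.**

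P(pass) = Σ over x = 2 to 11 of P(X1 = x) × P(X2 ≥ 7 − x)

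- p = 0.1: 0.0422
- p = 0.3: 0.8510, so the type II error is 1 − 0.851 = 0.149

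**3. Literal Section 9 rule: at least 2/11, then at least 7/24.**

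P(pass) = P(X1 ≥ 2) × P(X2 ≥ 7)

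- p = 0.1: 0.3026 × 0.00746 = 0.0023
- p = 0.3: 0.8870 × 0.6114 = 0.5423, so the type II error is 0.458

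**4. Comparison.**

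| True response rate | Cumulative | Literal | Difference |
|---|---|---|---|
| 10% (type I error) | 0.042 | 0.0023 | 0.040 |
| 30% | 0.851 | 0.542 | 0.309 |
| 40% | 0.968 | 0.877 | 0.091 |
| 50% | 0.994 | 0.983 | 0.011 |

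The smallest total that can pass is 7/35 (20%) under the cumulative rule and 2 + 7 = 9/35 (26%) under the literal one.

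**5. Which design do the stated numbers belong to?** An exhaustive search for Simon's optimal design (0.10 versus 0.30, type I error at most 0.05), with the final boundary counted over all patients, gives:

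| Type II error limit | Stage I: stop at or below | Final: fail at or below | Type I error | Power | Stage I stop at 10% | Expected N at 10% |
|---|---|---|---|---|---|---|
| 0.15 | 1/11 | 6/35 | 0.042 | 0.851 | 0.70 | 18.3 |
| 0.10 | 2/18 | 6/35 | 0.047 | 0.902 | 0.73 | 22.5 |

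The first row is the plan's design in every stated number, with the 6 counted over 35. Both rows end at 6/35, but the plan's 11 first-stage patients and its 0.70 match only the 0.15 row. The 0.1 in Section 9 therefore does not belong to the design that Section 9 describes.

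**The case against.** The strongest reply is that the documents already show what was meant. Section 4.2 names Simon's optimal design, the Abstract counts to the end of stage II, and the phrase in Section 9 can be read loosely as referring to the second-stage look. On that view 0.54 is the power of a rule nobody intended. The intent is indeed clear enough to identify the right correction, and the 0.54 applies only if the sentence is followed as written. But no text resolves the conflict, and the wording at fault sits in the statistical section, directly after the second stage is defined as 24 patients.

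The consequences are also bounded. The final rule applies after accrual is complete, so no enrollment stops early because of it. The literal rule is conservative and adds no false-positive risk. Response rates would be estimated either way, and the primary objective is phrased as estimation. All of that stands; the harm is limited to a wrong negative verdict. Section 9 nevertheless frames the trial as a hypothesis test, so that verdict matters.

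The 11/35 example is not typical. At a true rate of 30% the two rules disagree with probability 0.309. Totals of 11/35 or more account for 0.044 of this, and totals of 7 to 10 out of 35 (20% to 29%) for the other 0.264 (parts rounded separately). The size of the problem is the 0.309; the example only illustrates it.

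Finally, the type II error conflict could be settled instead by moving to 2/18 then 6/35, which reaches 0.902 power with the same total. Target power is the sponsor's choice. That route would change stage I in all three places, whereas restating 0.1 as 0.15 fits everything else already written.

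**Conclusion.** The concern holds. Section 9 misstates the final decision rule, and its type II error of 0.1 does not fit the design. If the rule were followed literally, power at 30% would be 0.542 instead of 0.851 and the type I error 0.0023 instead of 0.042. The loss shrinks to 0.091 at a true rate of 40%.

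The figures assume exactly 35 evaluable patients, a single common response rate across the pooled fusion types, and independent patients. That the cumulative count was intended is an inference from the Abstract wording and the match to the optimal design; the stage I stopping probabilities cannot establish it. The figures do not cover the extension in Section 4.2 ("until we have enrolled at least 5 patients for each of the 4 study drugs with a max of 50 patients enrolled"), for which no boundary is given.

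**What to change.** 1. In Section 9, replace the final-boundary sentence with one that counts all responses. For example: the trial is terminated if the total number of responders among the 35 evaluable patients, stages I and II combined, is 6 or fewer when the second stage ends.
2. Use that same sentence in the Abstract and in Section 4.2.
3. In Section 9, change the type II error from 0.1 to 0.15 to agree with Section 4.2. If the sponsor wants 0.10, the stage I size and boundary must be redesigned in all three places.
4. When making the edit, settle two things the new sentence depends on: which definition of evaluable supplies the 35 (Section 4.2 requires 8 weeks of treatment; Section 9 requires one cycle with at least 90% of doses), and whether patients enrolled beyond 35 enter the final test.

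Items 1 to 3 cost one sentence and one number in Section 9, plus matching wording in two other places. They need no additional patients or procedures.
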